During the 1-month quitting preparation phase, participants assigned to the *Media literacy* and *Combined* arms will be instructed to complete media literacy e-learning lessons. All participants will be instructed to complete the registration and setup text-messaging support program and begin preparing for quitting and be familiar with the remote saliva cotinine sample submission procedure for the abstinence phase. The 2-month abstinence phase starts with the day after the self-designated quit date (not later than the 1-month quitting preparation phase), where participants will engage with 3scheduled video calls at Week 6, Week 8, and Week 10 to conduct and submit a remote saliva cotinine testing result. The content of a video call is described as follows:

- At each video call, participants will be asked to submit a remote saliva cotinine sample to track their abstinence progress. Each call should take less than 20 minutes.
- During the video call, the research team will check-in with participants, and participants will then be instructed on how to complete the remote saliva cotinine sample submission as follows: (1) participants will open the new, labeled packaging for each testing kit while on the video call to ensure they are using a new test each time; (2) participants will be asked to write down the participant id, test number, date, and time on the test kit; and (3) participants will take a picture, including participant id, test number, date, and time for verifying the final results and provide the final results (approximately 10-minute processing time) and picture to the research team member before ending the call.

All participants will receive an evidence-based active text-messaging support program (i.e., This is Quitting; <https://truthinitiative.org/thisisquitting>).

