What are the potential risks associated with each research procedure, intervention, evaluation and/or test? If data are available, estimate the probability that a given harm may occur and its potential reversibility.

The risks associated with the measurements proposed in this study are minimal; these tests are not different from tests used in standard care for smoking/vaping/substance use individuals. Th saliva and urine nicotine samples are both non-invasive. The risks associated with the vaping cessation program consisting of education lessons and text-messaging support program (i.e., This Quitting) are minimal. Online questionnaires, live video call, and/or financial incentive may make participants uncomfortable, but they may choose not to answer any question, participate in the video call, or receive final rewards. Participants may experience some withdrawal symptoms due to initiating quitting. Moreover, for participants whose response for the mental health related question are above the threshold, the research team will provide resource at Nebraska Family Helpline at [contact].

In addition, the potential risk includes possible loss of confidentiality, which our team will strive to avoid by using de-identified data during statistical analysis, only giving individuals listed in this protocol access to the data collected, and storing all data on a password-protected computer.

Moreover, the risk of participation in the exit interview is minimal. The information shared with the study investigator or staff will be kept confidential to the fullest extent of the law, and the final reports will not include any identifying information. Some participants may be

uncomfortable in an interview setting though the focus on ways to improve cessation is not a highly reactive topic. There are also risks to the privacy and confidentiality of audio recordings. The seriousness of this risk is low. We believe the benefits to provide input to refine the vaping cessation program that can help improve young adult abstinence outcomes far outweigh the risks. These risks will be presented to the participants prior to participation, and if the subject is interested in study participation, informed consent will be obtained.

17. Risk Classification

What is the overall risk classification of the research?

♦ Minimal risk

Greater than minimal risk

18. Minimization of Risk

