A. Describe how the subjects of the research will be monitored by the investigators and other research personnel to ensure their safety.

The PI and the research team will be responsible for monitoring all aspects of the study and ensure the trial is conducted according to the approved protocol. Serious adverse events will be reported in a timely manner to the research team, if disclosed by a participant.

Reports on participation, engagement, retention, and participant flow will be provided to the PI for review on a weekly basis. In addition, during the 3 scheduled video calls (Week 6, Week 8, and Week 10), research staff will check in with participants to see if there is any question-related to the conduct of the study.

In addition, subjects will be notified that they may stop at any time if they feel any discomfort during the cessation process, and report any adverse events to the research team via email or the phone call.

For participants who participate in the exit interview, they will be informed before the interview that participation is voluntary and they may stop the interview at anytime.

B. Describe how the data collected will be monitored to ensure the safety of subjects.

Identify who will perform the ongoing data and safety analysis, and describe the frequency of data analysis. If there is an independent Data and Safety Monitoring Board (DSMB) provide the charter, or describe (1) the composition of the DSMB membership, (2) the frequency of DSMB meetings and reports.

Though participation in the intervention conditions and completion of assessment points are of minimal risk and participants are not masked, the study will monitor participation, engagement, and retention throughout the study period. The PI and the research team will be responsible for monitoring all aspects of the study and ensure the trial is conducted according to the approved protocol. Data will be reported to the PI and be reviewed together

with the research team to ensure the study is moving forward at the proposed rate. Serious adverse events will be reported in a timely manner to the research team, if disclosed by a participant. Reports on participation, engagement, retention, and participant flow will be provided to the PI for review on a weekly basis.

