Due to the low risk of the intervention program and the pragmatism of the pilot trial, the data and safety monitoring board will not be appointed. However, the data safety and monitoring plan will be tabulated and presented to the PI and the research team on a monthly basis. Participants will be asked to report any adverse events with the participation in the vaping cessation program at any time during the run-in phase and abstinence phase of the proposed trial or the contact with the research team. Participant reports on adverse event rates and participant receipt of intervention components will be reviewed by the PI and the research team on a monthly basis. Any deviations from participation, engagement, and retention projections will be discussed within the research team for review and possible action.

Given the low risk of adverse events as a result of participation in this study, it is unlikely that the rates of these events will necessitate stopping the trial. Nonetheless, the research team will monitor the rates of participant disclosure of any adverse events and report unexpectedly high rates to the IRB.

C. Describe the auditing plan for research conducted. Identify who will conduct the audits and specify the audit frequency.

The PI will review the data once a week to ensure it is being carried out according to the protocol submitted in this IRB application.

D. Describe the specific subject withdrawal criteria.

Individual subjects will not be removed from the research by the investigator unless they request to be removed from the study.

Moreover, participants will not be removed from the study if they do not complete a certain percentage of the required research procedures (do not complete education, do not register for the app, do not answer phone calls, etc.).

E. Describe the stopping rules for the research (e.g., the specific criteria for halting or early termination of the study).

Given the low risk of adverse events as a result of participation in this study it is unlikely that the rates of these events will necessitate the stopping of the trial. Nonetheless, we will monitor the rates of adverse events and report unexpectedly high rates to the IRBs. Other potential reasons to discontinue the trial, in an extreme case, could be: 1) that the treatment demonstrates a large magnitude of benefit, 2) that early in the trial we will be able to determine that there is no likelihood of demonstrating a treatment effect, 3) poor

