recruitment, or 5) poor retention of participants.

F. Describe plans and resources available to promptly address any subject injury.

Participants that experience a research-related injury will be encouraged to contact their primary care physician and contact PI or the research staff immediately. PI and the research team will review the case and communicate with participant's primary care physician for any followup.

In addition, participants will be asked to report any adverse events with the participation in the vaping cessation program at any time during the quitting preparation and abstinence phases of the proposed trial or the contact with the research team. Participant reports on adverse event rates and participant receipt of intervention components will be reviewed by the PI and the research team on a monthly basis. Any deviations from participation, engagement, and retention projections will be discussed within the research team for review and possible action.

19. Potential Benefits to the Subject

Is there the prospect for direct benefit (eg, research on diagnosis or treatment of disease)?

Yes

Describe potential benefits to the subjects that may reasonably be expected from participation in the research, if any. If there are therapeutic and non-therapeutic components of the research, address anticipated benefits to subjects that may reasonably be expected from each of these components.

Benefits may include complete cessation or reduction of use of tobacco and nicotine from e-cigarettes.

20. Potential Benefits to Society

Describe the potential benefits to society that may reasonably be expected to result from this research.

As there is limited research on how incentive-based and media literacy-informed approaches to facilitate vaping cessation (especially among young adults), this study may lead to novel multi-component interventions to increase the vaping abstinence rates.

ALTERNATIVES TO PARTICIPATION

21. Alternatives to Participation

1. Describe the likely care the subject would receive at this institution were he/she not to participate in the research. If there are more than one reasonable courses of treatment briefly describe.

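### No scheduled, uniform adverse-event or withdrawal question is described, so the disclosure rate reported to the IRB is likely to understate events (low severity)

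*Combined protocol and SAP*

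**What the plan says.** Section 16 (Potential Risks) states: "Participants may experience some withdrawal symptoms due to initiating quitting". It gives no expected frequency.

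Section 18.A, on monitoring subjects for safety, says that at the Week 6, 8 and 10 video calls "research staff will check in with participants to see if there is any question-related to the conduct of the study". On serious events, Sections 18.A and 18.B both say: "Serious adverse events will be reported in a timely manner to the research team, if disclosed by a participant". For other events, Section 18.A tells participants to "report any adverse events to the research team via email or the phone call".

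Section 12.B describes the same calls as a check-in followed by the saliva test: "the research team will check-in with participants, and participants will then be instructed on how to complete the remote saliva cotinine sample submission". It lists no symptom or adverse-event item and excludes none.

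Section 18.B adds: "Participants will be asked to report any adverse events with the participation in the vaping cessation program at any time during the run-in phase". Section 18.F repeats the request for the "quitting preparation and abstinence phases of the proposed trial or the contact with the research team". Neither section gives a question, form, schedule or symptom list.

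On escalation, Section 18.B says "the research team will monitor the rates of participant disclosure of any adverse events and report unexpectedly high rates to the IRB". Section 18.E describes the same monitoring as concerning adverse-event rates, without the reference to disclosure. No expected rate, denominator or threshold is given. No data and safety monitoring board will be appointed. Adverse-event reports go to the investigator and team monthly, while the weekly report covers participation, engagement, retention and participant flow.

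**The concern.** A disclosure rate is the product of two things: how often events happen and how often people mention them. The plan names a risk that it expects some participants to experience, yet describes no fixed moment at which everyone is asked about it. The calls are the only scheduled staff contacts between the quit date and the Week 12 visit, and the section on safety monitoring gives their purpose as questions about study conduct.

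Two things are at stake. First, the rate used to decide whether to alert the IRB could look unremarkable because few people volunteered anything. Second, Section 4.A says the pilot should inform whether the interventions can be scaled up. Event rates gathered without standard ascertainment are a poor basis for planning safety monitoring in a larger trial.

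**Working it through.** The plan states no adverse-event rate, expected rate, trigger or call-attendance figure, so there is no figure to reproduce. The check sets the sections side by side and then illustrates the direction of the effect on assumed inputs.

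**Where an event could be captured**

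| Place | What is described | Adverse-event or withdrawal question? |
|---|---|---|
| 12.B, video calls | Check-in, then saliva test | None listed |
| 12.B, baseline and end-of-study survey | Includes respiratory symptoms (12.D limits the symptom questionnaires to the 20 biomarker participants) | No withdrawal or general adverse-event item |
| 18.A, calls | Questions about study conduct | None listed |
| 18.A, outside calls | Email or phone, started by the participant | No; volunteered |
| 18.B and 18.F | Participants asked to report at any time, or at contact with the team | Ambiguous; no wording or timing |

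The last row can be read as a standing request or as a question put at each contact. If it is the second, Sections 12.B and 18.A do not carry it into the call content. Either way the sections need reconciling.

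**Timing.** Section 12.B puts the latest quit date at 30 days from baseline in one place and at the day after the one-month preparation phase (about day 31) in another. The engagement outcome ends that phase at Week 4 (day 28), which would make the day after it day 29. Week 6 is day 42. The gap from the latest quit date to the first scheduled call is 42 − 31 = 11 to 42 − 29 = 13 days. It is longer for anyone who quits earlier.

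**Understatement (illustration; all rates assumed).** Observed rate = true proportion × capture fraction. With N = 80, the expected number of participants recorded with an event is:

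| True proportion | 100% capture | 75% | 50% | 25% |
|---|---|---|---|---|
| 20% | 16 | 12 | 8 | 4 |
| 40% | 32 | 24 | 16 | 8 |
| 60% | 48 | 36 | 24 | 12 |

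For example, 80 × 0.40 × 0.50 = 16, an observed 20%. Suppose the team treated 24 of 80 (30%) as unexpectedly high; the plan sets no such number. With a true 40%, the exact binomial chance of recording at least 24 is 97.5% at full capture, 54.2% at 75%, 2.2% at 50% and below 0.01% at 25%.

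**Contact frequency and arm (illustration; all rates assumed).** Let p be the true proportion, b the capture by email or phone, s the capture of the remaining events at an attended call, and A the attendance. Observed rate = p × [b + (1 − b) × s × A]. With the same p in the incentive and non-incentive halves (40 each), the artificial difference is p × (1 − b) × s × (A₁ − A₀).

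- If s = 0 (calls surface nothing), the difference is 0 whatever the attendance.
- Largest case tried: 0.40 × 0.75 × 0.4 × (0.90 − 0.60) = 0.036, or 3.6 points (about 1.4 participants per 40).
- Smallest non-zero case tried: 0.40 × 0.50 × 0.2 × (0.90 − 0.75) = 0.006, or 0.6 points (about 0.2 participants per 40).

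Higher attendance in the incentive arms is plausible: Section 12.B pays only those arms for samples given on the calls, and the second hypothesis in Section 2 expects them to engage more.

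**The case against.** The best case for the plan is that Sections 18.B and 18.F do say participants will be asked to report events, and the mention of contact with the research team may mean asking at each call and visit. Section 12.B describes a general check-in, which does not rule out a question about symptoms. The consent form is not in the text available, so any reporting instructions in it cannot be judged. The study is classed as minimal risk and involves no drug, participants want to quit, and withdrawal is an expected effect. Other routes exist: a mental-health question with an action threshold (Section 16), timely reporting of disclosed serious events, and review of research-related injuries (Section 18.F). Neither the primary outcome nor its analysis is affected.

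Much of this stands. A reader might infer that staff ask about study conduct and nothing else, or that events count only if volunteered. The documents do not support either reading, given the 18.B and 18.F wording and the general check-in. A reader might also infer that the event rate is driven by arm-linked call attendance. That is not shown: if calls elicit nothing, attendance cannot affect the count, and the email and phone route is open to every arm. Nor is the disclosure rate the trial's only safety information.

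What does not stand is the idea that a standing invitation to report is equivalent to a question put to everyone at fixed times. No section describes such a question.

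**Conclusion.** The point holds as a gap in ascertainment, of low severity for a minimal-risk study. The plan names withdrawal as a risk but describes no uniform, scheduled question about it or about adverse events generally. The disclosure rate in Section 18.B, treated in Section 18.E as an adverse-event rate, is therefore likely to understate events. The direction follows from capture below 100%. The size cannot be derived from the documents, and every percentage in the illustration is an assumption.

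The possible dependence on contact frequency, and so on arm, is secondary. It arises only if events surface on calls, was 0.6 to 3.6 points over the assumed range, and feeds no planned analysis, because no between-arm safety comparison is specified.

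**What to change.** Reconcile the call content in Sections 12.B and 18.A with the reporting request in Sections 18.B and 18.F. Add one fixed question on adverse events and withdrawal symptoms since last contact, worded identically for all four arms and asked at the Week 6, 8 and 10 calls and the Week 12 visit. Record each answer in REDCap, including when nothing is reported. In Sections 18.B and 18.E, describe the monitored rate as based on this question and report it with the number of contacts as denominator.

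The cost is protocol wording, one short form and one to two minutes per existing contact. Reported counts will rise because people are being asked, and the team should expect that when judging what is unexpectedly high.

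Optional additions are the same item sent by REDCap link after a missed call, separate tables for solicited and volunteered events, and an adverse-event line in the weekly report.
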